8.5.2.2. Secondary anti-HBV Efficacy Analysis

The secondary anti-HBV efficacy endpoints include: (1) the proportion of subjects with HBV DNA < 29 copies/mL at Week 96, (2) the proportion of subjects with ALT normalization (i.e., subjects had ALT > ULN at baseline and a ALT ≤ ULN at the given post-baseline) at Weeks 48 and 96, and (3) the proportion of subjects with HBsAg loss at Weeks 48 and 96.

All these three anti-HBV efficacy endpoints will be analyzed using both Missing = Failure and Missing = Excluded approach. The 95% CIs will be constructed in the similar manner as described for the primary efficacy endpoint with stratification factors of HBeAg status (positive vs. negative) and baseline HBV DNA (< 8 log₁₀ IU/mL vs. ≥ 8 log₁₀ IU/mL).

8.6. Safety Analysis

All safety analyses will be performed using the safety analysis set.

All safety data collected on or after the date that the study drug was first administered up to the date of the last dose of study drug plus 30 days, unless specified otherwise will be summarized for subjects in the safety analysis set according to the study drug received.

Data for the pretreatment period and the period post the date of last dose of study drug plus 30 days will be included in data listings for all enrolled subjects.

8.6.1. Extent of Exposure

A subject's extent of exposure to study drug will be generated from the study drug administration page in eCRF. Exposure data will be summarized by treatment.

Duration of exposure to study drug will be expressed as the number of weeks between the first and last dose of the study drug, inclusive, regardless of temporary interruptions in study drug administration and summarized by treatment.

Dosing information for individual subjects will be listed.

8.6.2. Adverse Events

Clinical and laboratory adverse events will be coded using the Medical Dictionary for Regulatory Activities (MedDRA). System Organ Class (SOC), High-Level Group Term (HLGT), High-Level Term (HLT), Preferred Term (PT), and Lower-Level Term (LLT) will be attached to the clinical database.

Events will be summarized on the basis of the date of onset for the event. A treatment-emergent adverse event will be defined as any adverse event with onset date on or after the study drug start date and no later than 30 days after the study drug stop date; or any adverse event leading to study drug discontinuation.

Summaries (number and percentage of subjects) of treatment-emergent adverse events (by SOC, HLT [if applicable], and PT) will be provided by treatment. Additional summaries will include summaries for adverse events by grade, Investigator's assessment of relationship to study drug, and effect on study drug dosing.

On an ongoing basis adverse events will be reviewed for events that might meet the definition of Stage 3 Opportunistic Illnesses in HIV are indicative of an AIDS-Defining Diagnoses. The Gilead medical personnel will review the possible Stage 3 events and approve the events that meet the definition. Those events that do meet the Stage 3 Opportunistic Illness definition of an AIDS-Defining Diagnosis will be listed.

A listing of Stage 3 Opportunistic Illnesses in HIV can be found in [Appendix 7](#)

8.6.3. Laboratory Evaluations

Selected laboratory data (using conventional units) will be summarized using only observed data. Absolute values and changes from baseline at all scheduled visits will be summarized.

Graded laboratory abnormalities will be defined using the grading scheme defined in Grading of laboratory abnormalities attached in [Appendix 4](#).

Incidence of treatment-emergent laboratory abnormalities, defined as values that increase at least 1 toxicity grade from baseline at any time post baseline up to and including the date of last dose of study drug plus 30 days, will be summarized by treatment. If baseline data are missing, then any graded abnormality (ie, at least a Grade 1) will be considered treatment emergent. The maximum post baseline toxicity grade will be summarized by laboratory parameter.

Laboratory abnormalities that occur before the first dose of study drug or after the last dose of study drug plus 30 days will be included in a data listing.

8.6.4. Other Safety Evaluations

Vital signs will be summarized as appropriate.

8.7. Pharmacokinetic Analysis

Pharmacokinetic concentration data will be listed.

8.8. Sample Size

A total of approximately 240 HIV-1 and HBV co-infected subjects, randomized in a 1:1 ratio to 2 treatment groups (120 subjects per treatment group), achieves 90% power to detect a non-inferiority margin of 12% in Week 48 response rate (HIV-1 RNA < 50 copies/mL as defined by the US FDA-defined snapshot algorithm) difference between the 2 treatment groups. For the sample size and power computation, it is assumed that both treatment groups have a response rate of 91% (based on Gilead Studies GS-US-380-1489 and GS-US-380-1490), that the non-inferiority margin is 12%, and that the significance level of the test is at a one-sided 0.025 level.

A total of approximately 240 subjects also provides 81% power to detect a non-inferiority margin of 12% with respect to the co-primary efficacy endpoint of the proportion of subjects with plasma HBV DNA < 29 IU/mL at Week 48. It was assumed that both treatment groups have a response rate of 88% (based on Gilead Studies GS-US-320-0108 and GS-US-320-0110, with an assumption that 80% enrolled subjects were HBeAg negative and 20% were HBeAg positive), that the non-inferiority margin is 12%, and that the significance level of the test is at a one-sided 0.025 level.

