A total of approximately 240 HIV and HBV naïve, HIV-1 and HBV co-infected subjects, randomized in a 1:1 ratio to 2 treatment groups (120 subjects per treatment group), achieves 90% power to detect a non-inferiority margin of 12% in Week 48 response rate (HIV-1 RNA < 50 copies/mL as defined by the US FDA-defined snapshot algorithm) difference between the 2 treatment groups. For the sample size and power computation, it is assumed that both treatment groups have a response rate of 91% (based on Gilead Studies GS-US-380-1489 and GS-US-380-1490), that the non-inferiority margin is 12%, and that the significance level of the test is at a one-sided 0.025 level.

A total of approximately 240 subjects also provides 81% power to detect a non-inferiority margin of 12% with respect to the co-primary efficacy endpoint of the proportion of subjects with plasma HBV DNA < 29 IU/mL at Week 48. This assumes that both treatment groups have a response rate of 88% (based on Gilead Studies GS-US-320-0108 and GS-US-320-0110), that the non-inferiority margin is 12%, and that the significance level of the test is at a one-sided 0.025 level.

This study will be conducted in accordance with the guidelines of Good Clinical Practice (GCP) including archiving of essential documents.

GLOSSARY OF ABBREVIATIONS AND DEFINITION OF TERMS

° C	degrees Celsius
° F	degrees Fahrenheit
AE	adverse event
ALT	alanine aminotransferase
ANC	absolute neutrophil counts
ANOVA	Analysis of Variance
ARV	antiretroviral
AST	aspartate aminotransferase
AUC	area under the plasma/serum/peripheral blood mononuclear cell concentration versus time curve
BIC	bictegravir, B
B/F/TAF	bictegravir/emtricitabine/ tenofovir alafenamide, Bictarvy
BID	twice a day
BUN	blood urea nitrogen
CBC	complete blood count
CHB	chronic hepatitis B
CPT	Child-Pugh-Turcotte
CI	confidence interval
CL _{cr}	creatinine clearance
C _{max}	the maximum observed serum/plasma/peripheral blood mononuclear (PBMC) concentration of drug
CMH	Cochran-Mantel-Haenszel
CNS	central nervous system
COBI, /C	cobicistat
C _{tau}	the observed drug concentration at the end of the dosing interval
CPK	creatine phosphokinase
CRF	case report form(s)
CRO	contract (or clinical) research organization
CYP	cytochrome P450
DHHS	Department of Health and Human Services
DNA	deoxyribonucleic acid
DTG	dolutegravir, Tivicay®
ECG	electrocardiogram
eCRF	electronic case report form(s)
eGFR	estimated glomerular filtration rate
FAS	full analysis set
EVG	elvitegravir, E

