8.5.1.2. Analysis of Primary Efficacy Endpoint

The null hypothesis is that the proportion of subjects achieving HIV-1 RNA $<$ 50 copies/mL (as defined by the US FDA-defined snapshot algorithm) at Week 48 in B/F/TAF is at least 12% lower than the response rate in DTG + F/TDF; the alternative hypothesis is that the response rate in B/F/TAF is less than 12% lower than that in DTG + F/TDF.

Non-inferiority will be assessed using the conventional confidence interval approach. The point estimate of treatment difference (B/F/TAF – DTG+F/TDF) and the associated 2-sided 95% confidence interval will be constructed using a normal approximation method based on stratified Mantel-Haenszel proportions, where stratification factor include baseline HIV-1 RNA (\leq 100,000 copies/mL vs. $>$ 100,000 copies/mL).

It will be concluded that B/F/TAF is non-inferior to DTG + F/TDF if the lower bound of the 2-sided 95% CI of the difference (B/F/TAF – DTG+F/TDF) in the response rate is greater than -12%.

If non-inferiority of B/F/TAF to DTG+F/TDF is established, the lower bound of the 95% CI will be compared to 0; if the lower bound of the 95% CI is greater than 0, then superiority of B/F/TAF to DTG+F/TDF will be established.

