8.5.1.3. Analysis of Co-Primary Efficacy Endpoint for HBV

The null hypothesis is that the proportion of subjects with plasma HBV DNA < 29 IU/mL at Week 48 as determined by Missing=Failure approach in B/F/TAF is at least 12% lower than the response rate in DTG + F/TDF; the alternative hypothesis is that the response rate in B/F/TAF is less than 12% lower than that in DTG + F/TDF. For Missing = Failure approach, all missing data will be treated as HBV DNA \geq 29 IU/mL.

Non-inferiority will be assessed similarly as for the primary efficacy endpoint, except the stratification factors include HBeAg status (positive vs. negative) and baseline HBV DNA (< 8 log₁₀ IU/mL vs. \geq 8 log₁₀ IU/mL). To control type I error for the assessment of the primary and the co-primary efficacy endpoints, the hypothesis testing will be performed using the fallback procedure {[Wiens 2005](#)} in the sequential order with pre-specified 1-sided alpha level. The primary hypothesis of non-inferiority of B/F/TAF relative to DTG + F/TDF, with respect to the proportion of subjects with HIV-1 RNA < 50 copies/mL at Week 48 (as defined by the FDA snapshot analysis) will be tested first. Non-inferiority test will be performed at one-sided, 0.025 alpha level. If non-inferiority is established, the co-primary hypothesis of non-inferiority of B/F/TAF relative to DTG + F/TDF, with respect to the proportion of subjects with plasma HBV DNA < 29 IU/mL at Week 48 will be tested second at one-sided, 0.025 alpha level. Otherwise, the co-primary endpoint will not be tested at all.

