1.3. Sample Size and Power

A total of approximately 240 HIV-1 and HBV co-infected participants, randomized in a 1:1 ratio to 2 treatment groups (120 participants per treatment group), achieves 90% power to detect a non-inferiority margin of 12% in Week 48 response rate (HIV-1 RNA < 50 copies/mL as defined by the US FDA-defined snapshot algorithm) difference between the 2 treatment groups. For the sample size and power computation, it is assumed that both treatment groups have a response rate of 91% (based on Gilead Studies GS-US-380-1489 and GS-US-380-1490), that the non-inferiority margin is 12%, and that the significance level of the test is at a one-sided 0.025 level.

A total of approximately 240 participants also provides 81% power to detect a non-inferiority margin of 12% with respect to the co-primary efficacy endpoint of the proportion of participants with plasma HBV DNA < 29 IU/mL at Week 48. This assumes that both treatment groups have a response rate of 88% (based on Gilead Studies GS-US-320-0108 and GS-US-320-0110), that the non-inferiority margin is 12%, and that the significance level of the test is at a one-sided 0.025 level.

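### The 81% HBV power is for the HBV test taken alone; under the HIV-first testing rule the same calculation gives about 74% to 80%

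*Protocol*

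**What the plan says.** Protocol section 8.8 plans 120 subjects per arm and gives two powers, each for a 12% margin at one-sided 0.025. HIV has 90%, assuming 91% response in both arms. For HBV, "A total of approximately 240 subjects also provides 81% power to detect a non-inferiority margin of 12% with respect to the co-primary efficacy endpoint", assuming 88% response in both arms. The HBV rate comes from two HBV studies, "with an assumption that 80% enrolled subjects were HBeAg negative and 20% were HBeAg positive". The synopsis ("A total of approximately 240 subjects also provides 81% power to detect a non-inferiority margin of 12"%) and SAP section 1.3 ("A total of approximately 240 participants also provides 81% power to detect a non-inferiority margin of 12"%) repeat the HBV statement.

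The testing order is set out in the synopsis and protocol section 8.5.1.3. HIV is tested first at one-sided 0.025. If non-inferiority is shown, HBV is tested at one-sided 0.025. If not, "Otherwise, the co-primary endpoint will not be tested at all". The text calls this a fallback procedure but sets aside no alpha for HBV after an HIV failure, so the rule as written is a fixed sequence.

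Neither document gives the power for HBV under this rule, or a correlation between the two endpoints. SAP section 6.1.1 refers to a Week 48 SAP for the primary methods. That document was not available for this review.

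**The concern.** HBV DNA suppression at Week 48 is one of the two primary objectives. Under the HIV-first rule it can be claimed only if both tests succeed, and the probability of that cannot exceed the probability that the HBV test alone succeeds. A reader of section 8.8 or SAP section 1.3 would naturally take 81% as the planned chance of claiming HBV non-inferiority. If 81% is only the HBV-alone power, the design as written delivers less, by an amount that depends on a correlation the documents do not state. What is at stake is the accuracy of a planning figure that the final SAP still carries. No error rate or result is affected.

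**Working it through.** **Inputs** (protocol section 8.8 and SAP section 1.3): n = 120 per arm; margin 0.12; one-sided 0.025 for each test; response 0.91 (HIV) and 0.88 (HBV) in both arms. Missing data already count as non-response, so no separate dropout allowance applies. The alpha penalty in protocol section 8.9 moves HIV power by less than 0.01 point and is ignored.

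**Step 1: reproduce the stated powers.** Unpooled normal approximation: power = Φ(0.12 / √(2p(1−p)/n) − 1.96).

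- HIV: √(2 × 0.91 × 0.09 / 120) = 0.03695; 0.12 / 0.03695 − 1.96 = 1.288; Φ = 90.1% (stated 90%).
- HBV: √(2 × 0.88 × 0.12 / 120) = 0.04195; 0.12 / 0.04195 − 1.96 = 0.900; Φ = 81.6% (stated 81%).

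Both match, so 81% is the power of the HBV test with no condition on HIV. Exact enumeration of the unstratified Wald interval gives 90.2% and 81.9%.

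**Step 2: power under the HIV-first rule.** This is the bivariate normal probability that both tests succeed. The correlation between the two tests equals the within-subject correlation φ of the two binary outcomes, taken as the same in both arms.

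- Independent: 0.9011 × 0.8161 = 73.5%.
- Largest feasible φ: (0.88 − 0.91 × 0.88) / √(0.91 × 0.09 × 0.88 × 0.12) = 0.0792 / 0.0930 = 0.852.

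| φ | Power to conclude HBV non-inferiority |
|---|---|
| 0 | 73.5% |
| 0.3 | 75.2% |
| 0.5 | 76.6% |
| 0.852 (maximum) | 79.9% |

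Simulation with Wald intervals (400,000 trials per setting) gives about 74% at φ = 0 and 80.3% at the maximum. The most negative feasible value, φ = −0.12, gives 73.0%. Against the stated 81%, the gap is 81 − 73.5 = 7.5 points down to 81 − 79.9 = 1.1 points (0.7 by simulation at the top).

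**Step 3: a plausible place in the range.** Protocol section 1.2.3.4 reports 89.4% and 92.9% snapshot success in GS-US-380-1490, so failure was 10.6% and 7.1%. Under 1% of each arm had HIV-1 RNA at or above 50 copies/mL, which leaves more than 9.6% and 6.1% with no virologic data. Suppose 8 of the 9 planned points of HIV failure are missing data that also fail HBV, with independence otherwise. Then P(both respond) = 0.91 × 0.88 / 0.92 = 0.8704, φ = (0.8704 − 0.8008) / 0.0930 = 0.749, and the power is 78.8% (79.3% simulated). The sharing is an assumption. The snapshot uses on-treatment HIV-1 RNA only (section 8.5.1.1), while section 8.5.1.3 says "For Missing = Failure approach, all missing data will be treated as HBV DNA" at or above 29 IU/mL and sets no on-treatment limit.

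**Step 4: effect of stratification.** The planned interval is "constructed using a normal approximation method based on stratified Mantel-Haenszel proportions". For HBV the same method applies, "except the stratification factors include HBeAg status (positive vs. negative) and baseline HBV DNA". Using HBeAg only and the 80/20 mix, the variance per subject is v = 0.8·pₙ(1−pₙ) + 0.2·pₚ(1−pₚ), where pₙ and pₚ are the HBeAg-negative and HBeAg-positive rates. The documents do not give these rates. The three pairs below are assumptions, each averaging 88%, with HIV response 91% in both strata.

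| Negative / positive | v | HBV alone | Under HIV-first rule (independent to maximum φ) |
|---|---|---|---|
| 88 / 88 | 0.1056 | 81.6% | 73.5% to 79.9% |
| 92 / 72 | 0.0992 | 83.9% | 75.6% to 81.1% |
| 94 / 64 | 0.0912 | 86.8% | 78.2% to 81.9% |

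In every row the power under the rule is about 2 to 9 points below the HBV-alone power for the same inputs. Simulation with an HBeAg-stratified Mantel-Haenszel interval (200,000 trials) agrees to within about 0.2 points for the last two rows.

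**The case against.** Nothing stated is false: section 8.8 gives the power of a test at its own significance level, and 81% is right for that test. In the synopsis the testing rule stands shortly before the power statement, and both separate powers are given, so an attentive reader can see that joint success is less likely. This is true, but the reader still cannot obtain the figure, because the correlation is missing.

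The low end is weakly supported. Both viruses are measured at the same visits, and missing data count against both endpoints. In GS-US-380-1490 the Missing = Excluded and Missing = Failure denominators give 320 − 291 = 29 and 325 − 306 = 19 subjects without a Week 48 HIV-1 RNA value, or 48/645 = 7.4%, even with off-treatment results counted. Sharing 7.4 points gives about 78.2%. This stands as a reason to expect the upper part of the range, 2 to 3 points below 81%.

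The planned interval is stratified, and under the assumed HBeAg rates above, power at maximum correlation reaches 81.1% or 81.9%. This also stands: it is not established that power under the planned analysis is below 81%. But stratification raises the HBV-alone power too, and the gap between the two remains.

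Finally, Weeks 48 and 96 have been analysed, and this SAP covers only the final analysis, without between-group comparisons. So the correction changes no decision. It remains worth making because SAP section 1.3 still states the figure.

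**Conclusion.** The concern holds. The 81% is a correct HBV-alone power, presented without the condition that governs whether HBV is tested. By the unstratified calculation that reproduces the plan's figures, the power to conclude HBV non-inferiority is about 74% to 80%. It is about 78% to 79% if 7.4 to 8 points of missing data are shared by both endpoints. This rests on 91% and 88% response in both arms, a non-negative correlation and the HIV-first rule as written. Confidence is high for the unstratified figures. It is lower for the exact level under the stratified interval, which depends on HBeAg-specific rates the documents do not give. Type I error, the planned analysis and the Week 48 comparison are unaffected.

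**What to change.** In SAP section 1.3, and in protocol section 8.8 and the synopsis at any amendment, or otherwise in the clinical study report, add:

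> 81% is the power of the HBV test taken alone. Because HBV is tested only if HIV non-inferiority is shown, the power to conclude HBV non-inferiority is about 74% (independent endpoints) to 80% (largest feasible correlation) by the same unstratified calculation. The planned stratified interval may shift these figures.

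Optionally, call the procedure fixed-sequence, since no alpha is reserved for HBV; this changes the label only.

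The cost is two or three sentences and a less favourable planned power statement. No change to alpha, analysis, sample size or any conclusion is proposed.

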8.9. Data Monitoring Committee

An external Independent Data Monitoring Committee (IDMC) will review the progress, efficacy, and safety data of this study while the study is ongoing. The committee will convene after all subjects enrolled have completed their Week 24 visit or prematurely discontinued from the study drug. However, Gilead will defer to the IDMC for any decision to convene earlier or more frequently. The IDMC will examine the safety results of the trial and also focus on logistical issues such as accrual, retention, quality of clinical and laboratory data, and implications of results of external studies. Blinding will be preserved during the conduct of the study and access to unblinded data will be limited to designated parties.

No formal stopping rules will be used by the IDMC for safety outcomes. Rather, a clinical assessment will be made to determine if the nature, frequency, and severity of adverse events associated with a study regimen warrant the early termination of the study in the best interest of the participants.

For each IDMC analysis performed prior to the analysis of the primary efficacy endpoint, an alpha penalty of 0.00001 will be applied for the primary analysis of the primary endpoint.

8.10. Analysis Schedule

The Weeks 48 and 96 analyses will be conducted after all subjects either complete their Week 48 and 96 visits or prematurely discontinue from the study drug, respectively. The final analysis will be performed after all subjects complete the study or prematurely discontinue from the study.

9. RESPONSIBILITIES

9.1. Investigator Responsibilities

9.1.1. Good Clinical Practice

The investigator will ensure that this study is conducted in accordance with the principles of the Declaration of Helsinki (as amended in Edinburgh, Tokyo, Venice, Hong Kong, and South Africa), International Conference on Harmonisation (ICH) guidelines, or with the laws and regulations of the country in which the research is conducted, whichever affords the greater protection to the study subject. These standards are consistent with the European Union Clinical Trials Directive 2001/20/EC and Good Clinical Practice Directive 2005/28/EC.

The investigator will ensure adherence to the basic principles of Good Clinical Practice, as outlined in 21 CFR 312, subpart D, “Responsibilities of Sponsors and Investigators,” 21 CFR, part 50, 1998, and 21 CFR, part 56, 1998.

The investigator and all applicable subinvestigators will comply with 21 CFR, Part 54, 1998, providing documentation of their financial interest or arrangements with Gilead, or proprietary interests in the investigational drug under study. This documentation must be provided prior to the investigator’s (and any subinvestigator’s) participation in the study. The investigator and subinvestigator agree to notify Gilead of any change in reportable interests during the study and for 1 year following completion of the study. Study completion is defined as the date when the last subject completes the protocol-defined activities.

9.1.2. Institutional Review Board (IRB)/Independent Ethics Committee (IEC) Review and Approval

The investigator (or sponsor as appropriate according to local regulations) will submit this protocol, informed consent form, and any accompanying material to be provided to the subject (such as advertisements, subject information sheets, or descriptions of the study used to obtain informed consent) to an IRB/IEC. The investigator will not begin any study subject activities until approval from the IRB/IEC has been documented and provided as a letter to the investigator.

Before implementation, the investigator will submit to and receive documented approval from the IRB/IEC any modifications made to the protocol or any accompanying material to be provided to the subject after initial IRB/IEC approval, with the exception of those necessary to reduce immediate risk to study subjects.

